# **5.2** Definitions

5.2.1 Definition of Adverse Event. An adverse event (AE) is any untoward medical occurrence in a patient receiving study treatment and which does not necessarily have a causal relationship with this treatment. An AE can therefore be any unfavorable and unintended sign (including an abnormal laboratory

- finding), symptom, or disease temporally associated with the use of an experimental intervention, whether or not related to the intervention
- **5.2.2** Severity of Adverse Events. The severity of an AE is graded as follows:
- **5.2.2.1** Mild (grade 1): the event causes discomfort without disruption of normal daily activities.
- **5.2.2.2** Moderate (grade 2): the event causes discomfort that affects normal daily activities.
- **5.2.2.3** Severe (grade 3): the event makes the patient unable to perform normal daily activities or significantly affects his/her clinical status.
- 5.2.2.4 Life-threatening (grade 4): the patient was at risk of death at the time of the event.
- **5.2.2.5** Fatal (grade 5): the event caused death.
- **5.2.3** Serious Adverse Events. A "serious" adverse event is defined in regulatory terminology as any untoward medical occurrence that:
- **5.2.3.1** Results in death. If death results from (progression of) the disease, the disease should be reported as event (SAE) itself.
- 5.2.3.2 Is life-threatening. (the patient was at risk of death at the time of the event; it does not refer to an event that hypothetically might have caused death if it were more severe).
- 5.2.3.3 Requires in-patient hospitalization or prolongation of existing hospitalization for  $\geq 24$  hours.
- **5.2.3.4** Results in persistent or significant disability or incapacity.
- **5.2.3.5** Is a congenital anomaly/birth defect
- **5.2.3.6** Is an important medical event
- 5.2.3.7 Any event that does not meet the above criteria, but that in the judgment of the investigator jeopardizes the patient, may be considered for reporting as a serious adverse event. The event may require medical or surgical intervention to prevent one of the outcomes listed in the definition of "Serious Adverse Event". For example: allergic bronchospasm requiring intensive treatment in an emergency room or at

home; convulsions that may not result in hospitalization; development of drug abuse or drug dependency.

- 5.3 Steps to Determine If an Adverse Event Requires Expedited Reporting
- 5.3.1 Step 1: Identify the type of adverse event
- **5.3.2** Step 2: Grade the adverse event
- 5.3.3 Step 3: Determine whether the adverse event is related to the protocol therapy
- **5.3.3.1** Attribution categories are as follows:
- **5.3.3.1.1** Definite The AE *is clearly related* to the study treatment.
- **5.3.3.1.2** Probable The AE *is likely related* to the study treatment.
- **5.3.3.1.3** Possible The AE *may be related* to the study treatment.
- **5.3.3.1.4** Unrelated The AE *is clearly NOT related* to the study treatment.
- **5.3.3.1.5** Note: This includes all events that occur within 30 days of the last dose of protocol treatment. Any event that occurs more than 30 days after the last dose of treatment and is attributed (possibly, probably, or definitely) to the agent(s) must also be reported accordingly.
- 5.3.4 Step 4: Determine the prior experience of the adverse event. Expected events are those that have been previously identified as resulting from administration of the agent. An adverse event is considered unexpected, for expedited reporting purposes only, when either the type of event or the severity of the event is not listed in:
- 5.3.4.1 the current known adverse events listed in the Agent Information Section of this protocol;
- **5.3.4.2** the drug package insert;
- **5.3.4.3** the current Investigator's Brochure
- **5.4** Reporting Requirements for Adverse Events
- **5.4.1** Expedited Reporting. The Principal Investigator must be notified within 24 hours of learning of any serious adverse events, regardless of attribution, occurring during the study or within 30 days of the last administration of the study drug.
- 5.4.2 Routine Reporting. All other adverse events- such as those that are expected, or are unlikely or definitely not related to the study participation- are to be reported annually as part of regular data submission.

### **6** STATISTICAL CONSIDERATIONS

- **6.1** Public Deployment
- **6.2** Adherence Outcomes:
- 6.3 The primary outcome of Phase 1a will be rate of usage of each Intellicate application. This will be

examined by calculating standard descriptive statistics for the number of downloads and launches of each application. Secondary analyses of the primary outcome will include comparisons of co-usage of Intellicare application pairs, which we will test using Pearson correlations.

- **6.4** Field Trial
- **6.5** Power/sample size:
- 6.5.1 We estimate that we will have a 20% dropout, which will give us 80% power to detect effect sizes of 0.30. Power calculations were performed using Pass 2008.(Hintze, 2008)
- **6.6** Adherence Outcomes:
- 6.6.1 The primary outcome will be time to last use of a treatment element (lesson or tool), and will be tested between groups using traditional survival (Kaplan-Meier) methods, where the event of interest is last use from intervention start. Secondary analyses of the primary outcome would include Cox regression models that would adjust for potential effect modifiers or moderators such as gender, race, and age.
- **6.7** Patient Centered Outcomes:
- 6.7.1 Although power was presented for independent t-tests, primary analyses for patient centered outcomes (PHQ-9 and GAD-7) will utilize dependent t-tests
- **6.8** Mediation Analyses:
- 6.8.1 Mediators, such as app usage, we be examined in mediation models as time-varying covariates. We used the framework of Muller and colleagues(Muller, Judd, & Yzerbyt, 2005) to identify those variables, which mediate the effects of treatment on depression and anxiety. Only if the 4 criteria specified by Muller are satisfied (treatment effect for depression, treatment effect for the mediator, effect of mediator on depression, and reduction of treatment effect when mediator is included), will we calculate the effect of mediation using MacKinnon and colleagues' product of coefficients method.(MacKinnon, Lockwood, Hoffman, West, & Sheets, 2002) Bias-corrected 95% confidence intervals for the mediated effect will be calculated using bootstrapping.(Shrout & Bolger, 2002)
- 6.8.2 Development of the recommendation engine algorithms will use machine learning and Baysean. statistical methods that will continuously learn that will continuously learn from user interactions with IntelliCare to provide intervention recommendations.
- **6.9** Randomized Control Trial
- **6.9.1** Power/sample size:
- 6.9.2 Preliminary data indicates that approximately 50% of patients stop participating in BITs (which we define here as "drop out") by week 7 (see Sec. D.1.1). A sample size of 135/arm (total sample of 270) will provide 80% power to detect a difference in median drop out time from 7 to 10 weeks. We estimate from existing data (Sec D.1.1) that a 3 week increase would result in an 11% improvement in depression severity (ES=0.30). Additionally, this sample provides 80% power to detect an increase in continued participation from 50% to 61.6% at week 7. Both analyses are based on a log-rank test at a type 1 error rate of 5%, with accrual of 54 weeks and 12 weeks of intervention. Power for continuous patient

centered outcomes were based on independent t-tests, and would have 80% power to detect effect sizes of 0.34. Power calculations were performed using Pass 2008.(Hintze, 2008)

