#### PHASE 2: FIELD TRIAL

- 4.1.3 Phase II Field Trial. The purpose of the field trial will be twofold. The field trial will extend usability testing over time and under real life conditions. In addition, the field trial will be used to collect data to develop and evaluate machine learning methods. IntelliCare will be evaluated in up to 200 individuals meeting inclusion criteria in a 8-week, single arm field trial.
- Phase II Enrollment. Participants in the field-trial will be enrolled remotely to avoid excluding 4.1.3.1 participants with access barriers who are among those who would be likely end users. Interested parties will complete a brief telephone or web screen to determine whether there is any reasonable expectation that they might be eligible (data from the brief screen will be included in the study dataset). If they are clearly not eligible they will be informed of this and thanked. If they are eligible they will initiate the consent process. Following the initial pre-consent screening phone call but prior to the eligibility interview, the participant will be emailed a link to the detailed digital version of the consent form. Subjects agree to participate by checking a yes box and typing in their name. They are instructed to print out the consent form for their records. After the study consent form is signed online, detailed information regarding the consent will be reviewed with the participant and witnessing of the consent form will take place at this time by study staff. A date and time for the screening assessment will then be scheduled. An RA will then conduct an eligibility interview with the participant over the phone, where the MINI, HAM-A, and QIDs are administered. Questionnaires will be administered to patients via a secure web based assessment portal, so that the other inclusion and exclusion criteria can be determined. Patients will be paid \$20 for completing the eligibility interview. Payments may be made in either Amazon credits or by check depending on participant preference, NU payment policies, and payment availability at the time of study participation.

If eligible, a research study assistant will work with participants to download the IntelliCare system from the Google Play store. Eligible participants will include those who already own an Android smartphone with an operating system sophisticated enough to support the IntelliCare system (version 4.2.2 or higher).

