- Phase II Assessment, Measures & Compensation. Participants in the field trial will receive telephone-4.1.3.3 based interview evaluations and complete online self-report questionnaires at baseline, week 4 and week 8. All assessments and evaluations will be conducted by an RA who is blind to the treatment (i.e. coaches will not perform assessments on patients they coach). Depression will be measured at baseline by telephone interview using the QIDS-C for severity of symptoms and the MINI MDE module for diagnosis. Self-reported depression will be measured at baseline, wk4 & wk8 using the PHQ-9 administered online. Anxiety will be measured by telephone interview using the HAM-A for severity of symptoms at baseline. Self-reported anxiety will be measured using the GAD-7 administered online at baseline wk4, and wk8. Adherence will be assessed through use data from phone or other platforms (e.g. computer), including number of times the program was accessed, number of times each lesson, tool, and feedback element was accessed and percentage of messages viewed. The first 20 participants will also be engaged in extended usability testing, and will speak with a research assistant weekly, who will inquire into usability problems. We will compensate \$70 to each of the 200 field trial participants for taking part in their follow up assessments (Week 4 and Week 8). Participation in the trial may include the use of texting, and as such, study staff will reimburse participants who do not already have an unlimited monthly texting plan for their upgrade to such. Reimbursement of up to \$30 per month enrolled in the trial (up to two months) is possible. We will not be compensating participants who already subscribe to unlimited texting in their monthly plans. This decision was made in attempt to make the intervention more generalizable, so as not to overincentivize certain users by compensating them for matters already routine to them. Payments may be made in either Amazon credits or by check depending on participant preference. NU payment policies. and payment availability at the time of study participation.

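### The field trial's stated 80% power at effect size 0.30 cannot be reproduced from its inputs and is attributed to a test that a single-arm design cannot use

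*Combined protocol and SAP*

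**What the plan says.** The only power statement for the field trial is in section 6.5.1: "We estimate that we will have a 20% dropout, which will give us 80% power to detect effect sizes of 0.30". The sole other detail there is the software used.

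The design is in section 4.1.3: "IntelliCare will be evaluated in up to 200 individuals meeting inclusion criteria in a 8-week, single arm field trial". Section 4.1.3.3, on compensation, refers to "each of the 200 field trial participants", so 200 is the working figure as well as the ceiling.

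The analysis is in section 6.7.1: "Although power was presented for independent t-tests, primary analyses for patient centered outcomes (PHQ-9 and GAD-7) will utilize dependent t-tests". That sentence acknowledges that the powered test and the planned test differ, but no power figure is given for the planned one.

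**The concern.** A single arm measured at baseline, week 4 and week 8 has no second group, so an independent t-test does not fit it. The planned analysis is a within-person comparison. Its effect size is on a different scale (mean change over the SD of change) from that of a between-group comparison (mean difference over the raw SD). Section 6.5.1 does not say which scale 0.30 is on.

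This statement is the field trial's whole sample-size justification. If it does not follow from the stated enrolment and dropout, the reader cannot tell what size of pre-post change the trial was planned to detect, or why 200 was chosen.

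**Working it through.** **Inputs**
- Enrolled: 200 (sections 4.1.3 and 4.1.3.3; the former says up to 200).
- Dropout: 20% (section 6.5.1), so completers = 200 × 0.80 = 160.
- Stated result: 80% power at 0.30 (section 6.5.1).
- Alpha and sidedness: not stated for the field trial. Two-sided 5% is assumed.

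**Basis for two-sided 5%.** Section 6.9.2 gives a 5% level for the RCT's log-rank tests. It also says that power for its continuous outcomes, "centered outcomes were based on independent t-tests, and would have 80% power to detect effect sizes of 0.34". With 135 per arm, the normal approximation is (1.960 + 0.842) × √(2/135) = 2.802 × 0.1217 = 0.341. The exact noncentral-t value is 0.342, which reproduces the RCT figure. A one-sided 5% test would give 0.303. So two-sided 5% is the plan's convention elsewhere.

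**Planned paired t-test, 160 completers.** Detectable effect ≈ 2.802/√160 = 2.802/12.65 = 0.221; exact, 0.223 SD of the change score. At 0.30 the noncentrality is 0.30 × 12.65 = 3.79 and the power is 96.5%. The stated 80% is not reproduced.

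**Completers needed for 0.30, paired.** (2.802/0.30)² ≈ 87; exact, 89.1, so 90. Enrolled: 90/0.80 = 112.5, so 113.

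**Independent t-test, 160 baseline against 160 follow-up values.** Detectable effect ≈ 2.802 × √(2/160) = 0.313; exact, 0.314. Power at 0.30 is 76.3%. An independent test needs 176 per group for 80% at 0.30.

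**Other conventions**

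| Test | n | Level | Power at 0.30 | Detectable at 80% |
|---|---|---|---|---|
| Paired | 160 | one-sided 5% | 98.4% | 0.197 |
| Paired | 160 | two-sided 2.5% | 93.6% | 0.246 |
| Paired | 160 | two-sided 1% | 88.1% | 0.273 |
| Paired, dropout ignored | 200 | two-sided 5% | 98.8% | 0.199 |
| Independent | 160 + 160 | one-sided 5% | 84.9% | 0.279 |
| Independent, dropout ignored | 200 + 200 | two-sided 5% | 84.9% | 0.281 |
| Independent, dropout ignored | 200 + 200 | two-sided 2.5% | 77.3% | 0.309 |

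None comes within 2 points of 80%.

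**If 0.30 is in baseline-SD units.** With equal SDs at both times and pre-post correlation ρ, the SD of change is √(2(1−ρ)) baseline SDs, so the paired detectable effect is 0.2228 × √(2(1−ρ)):

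| ρ | Detectable effect (baseline SD) | Power at 0.30 |
|---|---|---|
| 0 | 0.315 | 76.0% |
| 0.3 | 0.264 | 89.0% |
| 0.5 | 0.223 | 96.5% |
| 0.7 | 0.173 | 99.8% |

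Power is exactly 80% at ρ = 1 − (0.30/0.2228)²/2 ≈ 0.09. The documents give no correlation.

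**The case against.** The strongest reply is that section 6.5.1 leaves so many inputs open that 0.30 cannot be called wrong. This stands in part. Enrolment of up to 200 is a ceiling, and a paired test does detect about 0.30 with 112 or 113 enrolled. A paired test of 160 also detects 0.30 in baseline-SD units if the pre-post correlation is about 0.09. A reader might therefore infer that 0.30 is an error under every reading, and the documents do not support that. They support only that it does not follow from 200 enrolled and 20% dropout under the usual conventions. No passage gives an enrolment near 113 or any correlation.

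A reader might also split the 160 into two groups of 80, obtaining a detectable effect of 0.446 and 47% power at 0.30. Nothing in the plan describes such a split. The more natural misapplication, 160 values against 160, misses only narrowly.

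It can also be said that section 6.7.1 discloses the change of test. It does, but it does not restate the power. Its opening clause recurs in the RCT's section 6.11.1, where independent arms exist. The wording may have been carried over, though the documents do not say so; if it was, it is weak evidence of how 0.30 was obtained.

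Finally, section 4.1.3 gives the field trial's purposes as extended usability testing and collecting data for machine learning, and any observed change would be read from its estimate and interval. That limits the consequence but does not make the statement correct.

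**Conclusion.** The point holds as one of reproducibility and consistency. The 80% power at 0.30 does not follow from 200 enrolled, one arm and 20% dropout, and the test to which section 6.7.1 attributes it does not fit the design. Under two-sided 5%, the paired test with 160 completers detects 0.22 SD of change.

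A reader might infer that the field trial is underpowered. The figures show the opposite in SD-of-change units, where power at 0.30 is well above the stated 80%. In baseline-SD units the same holds for any correlation above about 0.09; at zero correlation power would be 76.0%.

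The conclusion rests on 200 being the actual enrolment target, on a two-sided 5% level inferred from the RCT section, and, for the 0.22 figure, on effect size being in SD-of-change units. The mismatch between the independent test and the single arm needs none of these assumptions.

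**What to change.** Restate section 6.5.1, for example: *With 200 enrolled and 20% dropout (160 completers), a paired t-test at two-sided 5% has 80% power to detect a mean change of 0.22 SD of the change score.* The level, sidedness and SD basis in that sentence are assumptions for the sponsor to confirm. If the sponsor means baseline-SD units, the assumed pre-post correlation should be stated and the figure recomputed. If fewer than 200 are to be enrolled, the figure should be recomputed for that number.

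In section 6.7.1, delete the opening clause on independent t-tests, so that the sentence simply names the paired analysis.

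The cost is two sentences of wording and a short calculation. Sample size, data collection and planned analysis are unchanged.

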#### 3 PARTICIPANT ELIGIBILITY

- 3.1 Inclusion Criteria:
- 3.1.1 Meets criteria for clinically significant symptoms of depression and or anxiety using self-report measures used in screening for depression and anxiety as well as interviewer administered measures.
- 3.1.2 Is familiar with the use of mobile phones
- 3.1.3 Has an Android phone with at least a basic data plan and messaging plan and an operating system sophisticated enough to support the IntelliCare system
- 3.1.4 Is able to speak and read English;
- 3.1.5 Is at least 18 years of age (except in Nebraska where the age of consent is 19).
- 3.1.6 Is a United States Citizen/Resident
- **3.2** Exclusion Criteria:
- **3.2.1** Has visual, hearing, voice, or motor impairment that would prevent completion of study and treatment IRB# STU00074405 Version 11.29.2017

[figure not shown]
procedures;

- 3.2.2 Is diagnosed with a psychotic disorder, bipolar disorder, dissociative disorder, substance or alcohol dependence, or other diagnosis for which participation in this trial is either inappropriate or dangerous;
- 3.2.3 Is severely suicidal (has ideation, plan, and intent). Although procedures with back-up plans are in place for patients who develop suicidality, the highly experimental nature of this intervention makes enrollment of severely suicidal patients unethical;
- 3.2.4 Participants who have been on an antidepressant or anxiolytic medication with no dose changes for 14 days and do not intend to change the dose will be eligible. Those who have been on the antidepressant for less than 14 days or intend to have their medication optimized will be asked to wait for screening until they meet the 14-day criterion
- 3.2.5 Has used any of the IntelliCare apps more than one time in the last 3 months.

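### The field trial's mediation analysis (6.8.1) requires treatment effects that a single-arm study cannot estimate, and the pre-post change in 6.7.1 is not a valid substitute

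*Combined protocol and SAP*

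**What the plan says.** Section 4.1.3 describes Phase II as a study of "up to 200 individuals meeting inclusion criteria in a 8-week, single arm field trial". It gives two purposes: "The field trial will extend usability testing over time and under real life conditions", and "the field trial will be used to collect data to develop and evaluate machine learning methods". Entry criterion 3.1.1 is "Meets criteria for clinically significant symptoms of depression and or anxiety using self-report measures used in screening for depression and anxiety", together with interviewer-administered measures. Section 4.1.3.3 schedules the PHQ-9 and GAD-7 at baseline, week 4 and week 8.

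Under the Field Trial heading in section 6, 6.7.1 states that "primary analyses for patient centered outcomes (PHQ-9 and GAD-7) will utilize dependent t-tests". Section 6.8.1 names app usage as an example of a mediator and applies a published framework "to identify those variables, which mediate the effects of treatment on depression and anxiety". The mediated effect is calculated only if four conditions hold: treatment affects depression; treatment affects the mediator; the mediator affects depression; and the treatment effect shrinks once the mediator is in the model.

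For this phase the documents describe no control group, run-in, repeat baseline or external benchmark, and no caution about attributing change to IntelliCare.

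**The concern.** A treatment effect is a contrast between what happened under treatment and what would have happened without it. In the field trial everyone is treated, so the data contain no such contrast, for symptoms or for app use. Three of the four conditions in 6.8.1 name a treatment effect or its reduction.

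The analyst then has two choices. One is to conclude that the conditions cannot be evaluated, in which case a planned analysis is empty. The other is to let change from baseline stand in for the treatment effect. Participants enter with elevated symptoms, so some fall is expected even if the apps do nothing. App use must rise from almost nothing in anyone who installs the apps. The first two conditions could then be passed for reasons unrelated to any effect, and app use reported as a mediator with a bootstrap interval around a quantity that has no causal meaning.

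**Working it through.** **1. What one arm can supply for each condition in 6.8.1**

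- Treatment effect on depression: not estimable. Only the mean change from baseline is available.
- Treatment effect on the mediator: not estimable. Criterion 3.2.5 excludes people who used any IntelliCare app more than once in the last 3 months, so use starts near zero for all. Change in use is fully confounded with time since installation.
- Mediator on depression: estimable as an association only.
- Reduction of the treatment effect when the mediator is included: not estimable, because the first quantity is missing.

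This is the core of the point and needs no arithmetic.

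**2. How far the stand-in could be from zero with no treatment effect**

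The plan gives no figure for this, and no Phase II cutoff, screening SD or retest correlation. What follows is an illustration.

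Inputs from the documents:
- Up to 200 participants (4.1.3) and 20% dropout (6.5.1): 200 × 0.80 = 160 completers.
- The only numeric symptom rule in the documents is for Stage 1b (4.1.2.3.1): PHQ-8 of at least 10, or GAD-7 of at least 8. It is borrowed here and applied to PHQ-9 and GAD-7, with continuity-corrected limits of 9.5 and 7.5.

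Assumptions not in the documents: PHQ-9 SD 5.5; GAD-7 SD 5; screening means 8 to 12 (PHQ-9) and 5 to 11 (GAD-7); correlation between scales 0.5 to 0.7; PHQ-9 retest correlation r 0.7 to 0.85; normal scores; two-sided 5%; no natural recovery.

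Formulas, where X is the baseline PHQ-9, μ its screening mean and S the selected group:
- expected fall = (1 − r) × (E[X | S] − μ)
- SD of change = √{(1 − r)² Var(X | S) + 5.5² (1 − r²)}
- dz = fall / SD of change; rejection rate = power of the paired t-test at dz with n = 160

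E[X | S] and Var(X | S) were obtained by simulating the either/or rule.

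| PHQ-9 / GAD-7 means | scale corr. | r | E[X given S] − μ | fall | SD of change | dz | rejection |
|---|---|---|---|---|---|---|---|
| 8 / 5 | 0.7 | 0.70 | 4.30 | 0.30 × 4.30 = 1.29 | 4.09 | 0.315 | 98% |
| 10 / 8 | 0.6 | 0.80 | 2.45 | 0.20 × 2.45 = 0.49 | 3.42 | 0.143 | 44% |
| 12 / 11 | 0.5 | 0.85 | 1.12 | 0.15 × 1.12 = 0.17 | 2.99 | 0.056 | 11% |

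The range is about 0.2 to 1.3 points and 11 to 98%, against a nominal 5%.

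**3. Why the either/or matters**

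Applying only the PHQ half of the borrowed rule gives larger values. At mean 10 and r = 0.8, c = (9.5 − 10)/5.5 = −0.09, and the fall is 0.2 × 5.5 × φ(c)/(1 − Φ(c)) = 0.82 points, with dz 0.24 and 86% rejection. The either/or rule gives 0.49 points and 44% at the same PHQ-9 mean and r, because people admitted on GAD-7 alone have lower PHQ-9 scores at entry. The 86% figure should not be used.

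**The case against.** The strongest reply is that Phase II claims no efficacy. Section 6.7.1 names a test of change and attributes nothing to the apps; the efficacy hypotheses in 2.1.3 belong to the randomized trial; and the power statement in 6.9.2 cites other preliminary data, so no documented decision rests on the field-trial change. This stands for 6.7.1, which needs only a caveat. It does not rescue 6.8.1, whose own wording speaks of treatment effects.

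A second reply is that 6.8.1 may be wording carried over from 6.12.1. Section 6.6.1 likewise mentions a comparison between groups in a one-arm study. That is plausible, but 6.8.1 adds app usage and anxiety to the RCT text, and it is operative wherever it came from.

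Third, nothing in the documents says that the paired test supplies the treatment effect for the mediation conditions. That is correct: the link is an inference from the lack of any other candidate, and on a literal reading no mediated effect would be calculated at all.

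Fourth, the size is uncertain. Section 4.1.3.1 describes a brief screen, then an interview with the MINI, HAM-A and QIDS, then questionnaires. If selection rests partly on an earlier screen or on other instruments, baseline PHQ-9 regresses less than modelled. As to concurrent care, 3.2.4 requires 14 days without a dose change and no intention to change, which limits medication as a source of change without excluding it. Both limits are accepted.

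Finally, a 95% CI for mean change carries the same information as the paired t-test. That is true, and the test need not be removed.

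**Conclusion.** The mediation analysis in 6.8.1 cannot be carried out as written in a single-arm study and should be corrected. This conclusion rests on the design alone. Section 6.7.1 needs a statement about interpretation, not a different method.

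A reader might infer more: that the paired test will probably be significant whether or not IntelliCare works. The documents do not support that from regression to the mean alone. With no Phase II cutoff, SD or retest correlation, the illustrative rejection rate runs from 11% to 98% and depends mainly on how symptomatic the screened population is and how entry is decided. Every scenario shown exceeds 5%, and natural recovery, which is not quantified here, would add to the fall. A reader might also infer that 6.7.1 asserts efficacy or that its result feeds the RCT sample size; the text says neither.

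The power statement in 6.5.1 is a separate matter and does not bear on this point.

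**What to change.** In 6.8.1, delete treatment-effect mediation for Phase II and state that mediation of treatment is examined in the randomized phase under 6.12.1. Section 6.12.1 mentions depression only, so add anxiety there if it is still wanted, in line with objective 2.2.1.

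If an analysis of use in Phase II is wanted, specify the association of app use up to week 4 with the week-8 score, adjusted for the week-4 score. Label it non-causal, since people who keep using the apps may differ from those who stop.

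In 6.7.1, report mean change in PHQ-9 and GAD-7 with 95% CIs. The paired t-test may stay. Add one sentence saying that this is uncontrolled change in people selected for elevated symptoms and is not attributable to IntelliCare.

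The cost is wording only: the week-4 and week-8 scores and the use data are already collected under 4.1.3.3. The downside is that the field trial makes no efficacy or mediation claim, which its stated purposes of usability and data for machine learning do not require.
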